This study is a single-center, simple random parallel group design clinical trial, each random group is allocated according to the proportion of 1:1:1.

IV. Clinical trial site

Responsibilities: Second Affiliated Hospital of Zhejiang University; [name];
[contact];

Address: [name]
Province; [name]

Participation Unit: the Second Affiliated Hospital of Zhejiang University Medical College; person in charge: [name]

V. Design of research

1. Inclusion criteria

(1) Age 18-80 years old; (2) a teeth choice: 6-8 weeks after the teeth after the periodic treatment of teeth, there is at least one site periodontal diagnosis depth (PD) ≥ 5 mm, looseness is less than II The degree or II-III degree will be loose after a fixed fixed, imaging evaluation of the vertical bone absorption of the teeth is greater than 3 mm osteogenesis, and the site is free of teeth surgical treatment, the patient has no obvious symptoms; (3) Patients have better compliance, and the bacterial plaque control is good after the basic treatment (all-in-law bleeding index and the mushroom index), can understand the purpose of testing, willing to cooperate with surgery and follow-up, voluntarily participate in the test and signed Informed consent.

2. Exclusion criteria

(1) In the past 6 months, chewing smokeless tobacco, smoking or suction cigar once a week or more, or smoking more than 20 / week (1 pack / week); (2) patients before blood Three months taking any drug or platelet counts that affect platelet function less than 200,000 / mm³; (3) patients have taken anti-epileptic drugs, antiplasia, antidepressants, sedatives, califiers, anti-depression, sedatives in the

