The newly diagnosed patients were recalled after 6-8 weeks of basic treatment to evaluate whether they met the inclusion exclusion criteria and confirm the operation site. For the patients considering inclusion, they agreed on the operation time one week later (female patients avoided menstruation). Oral health education was given to the patients again. One week later, the operative (V0), the informed consent form was signed by the patient, and then the researchers measured the baseline of the included patients, including (1) clinical periodontal index: probing depth (PD), clinical attachment level (CAL), mobility

(mobility), probing bleeding (BOP). (2) Imaging examination: the height of bone defect (IC), bone level (RBL) and the angle of intraosseous defect were measured by CBCT image, and the volume of intraosseous defect was measured after three-dimensional reconstruction of the affected teeth: all measurements were repeated twice to take the average value; before the actual measurement, all measurement researchers have passed the consistency test. Researcher A uses a random number table for random grouping and uses opaque sealed envelopes for distribution and concealment, and then hands over the envelopes to researcher B and no longer participates in the follow-up study. Researcher B numbered the enrolled patients 1-78 in order. Before the operation, researcher B handed over the sealed envelope to the itinerant nurse to open it, and both the patient and the patient were blind at this time. Since then, researcher B is responsible for supervising the operation. All the operations were performed by experienced surgeons. The surgical area was anesthetized before operation, intraoral and perioral routine disinfection was performed, and the operation was carried out in accordance with the principles of routine periodontal regeneration and aseptic operation.

If the patient was assigned to the APRF+GTR group, 20ml was collected with a blood collection needle from the superficial elbow vein immediately before operation and placed in two special glass centrifuges for APRF. Immediately after the blood collection was completed, the blood was symmetrically placed in the TR-18plu series centrifuge, and the 14min was centrifuged with 1500rpm at room

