was completed, the symmetrical Medifuge centrifuge was selected, and the CGF procedure was selected and centrifuged for 13 minutes. The CGF centrifugation procedure is as follows: accelerate for 30 seconds, rise to 2700r/min, centrifuge for 2 minutes, then descend to 2400r/min, centrifuge for 4 minutes, accelerate to 2700r/min, centrifuge for 4 minutes, then descend to 3000r/min, centrifuge for 3 minutes, and decelerate to stop in the last 36 seconds. Finally, the blood in the test tube is divided into three layers: the top layer is PPP, the lowest layer is crimson jelly-like red blood cells and platelets, and the middle layer is yellow translucent gel-like CGF. The 2 test tubes completed by centrifugation were placed vertically on the operating compartment table for backup (not tilted or inverted). The APRF gel in the above process was changed to CGF gel, mixed and covered with CGF, and the other operations were the same.

If the patient was assigned to the GTR group, no blood was drawn. Gel or membrane containing growth factor was not used to cover the operation, and the rest of the operation was the same.

At the end of the operation, the surgeon gave the patient postoperative medical advice and given postoperative medication: cefuroxime axetil 50mg, ornidazole 500mg, twice a day for 5-7 days. Oral hygiene education was given to the patients again, and patients were advised to use Koutai mouthwash twice a day for 2 weeks, and about 2 weeks later to remove stitches. Two weeks after operation, stitches were removed by the original surgeon, and the patients were scheduled for 12 weeks \pm 7 days (V1), 24 weeks \pm 14 days (V2) and 48 weeks \pm 28

days (V3).

VII. Observation index and evaluation of curative effect

The patients were contacted and followed up by researcher B at 12, 24 and 48 weeks after operation. At 12 weeks \pm 7 days after operation, PD, CAL, mobility and BOP were measured by measurement researchers. 24 weeks \pm 14 days and 48 weeks \pm 28 days after operation, the researchers measured PD, CAL, mobility, BOP, RBL, IC, intraosseous defect angle and bone defect volume.

PD (probe depth) :use a periodontal probe (UNC-15,Hu-Friedy,Chicago,IL) paralleling to the long axis of the tooth to measure the distance from the bottom of the periodontal pocket to the gingival margin (mm), record six sites of each tooth (the mesial, median and distal site of the buccal and tongue surface).

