CAL (clinical attachment level) : The distance from periodontal pocket bottom to CEJ was measured by periodontal probe (mm). Record six sites of each tooth (the mesial, median and distal site of the buccal and tongue surface).

mobility: use a tweezer to clamp the incisal areas of the anterior teeth or the pit groove on the occlusal surface of the posterior teeth and shake the teeth faciolingually, mesiodistally and vertically. I degree : abnormal mobility faciolingually or less than 1mm positioning. II degree : abnormal mobility faciolingually and mesiodistally or loosening range of 1-2mm. III degree : abnormal mobility faciolingually, mesiodistally and vertically or loosening range is

greater than 2mm.

BOP(bleeding of probe) : observe for 10-15 seconds after probe to see whether it bleeds. Record six sites of each tooth (the mesial, median and distal site of the buccal and tongue surface).

RBL(radiographic bone level): Locate the reference point at the deepest PD site of the affected tooth: cemento-enamel junction (CEJ), alveolar crest (AC), bone defect (BD) .RBL is the straight line distance from CEJ to BD (mm)

IC: IC is the straight line distance from AC to BD (mm)

regenerated bone volume parameters : in mimics software, threshold was set according to the gray value of the affected tooth and its surrounding alveolar bone, image editing and region growth were used to form a mask of the three-dimensional reconstruction area. The three-dimensional calculation function was used to reconstruct the three-dimensional shape of the alveolar bone in the target area. Furthermore, the structure of alveolar bone was optimized by remeshing and smooth. The volume of alveolar bone before and after operation was calculated by Boolean operation to obtain the model of regenerated alveolar bone and its volume was measured.

Defect fill (%) = (preoperative IC- and postoperative IC) / preoperative IC × 100%

Defect resolution (%) = (preoperative RBL- and postoperative RBL) / preoperative RBL × 100%

VIII. Statistical analysis method (statistical software: SPSS25.0)

1) data description: measurement data are described by mean \pm standard

deviation, non-normal distribution data are described by median and percentage (25th 75th percentile)

(2) baseline data are compared with normal distribution by one-way ANOVA test, while measurement data of non-normal distribution are described by Wilcoxon rank sum test.

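### IC is labelled the defect's height but defined as the straight line from crest to base, so Defect fill (%) mixes vertical fill with defect width

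*Combined protocol and SAP*

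**What the plan says.** The combined protocol and SAP describes IC in two ways. Section VI.3 (Treatment scheme), listing the baseline imaging, calls it "the height of bone defect (IC"). Section VII (Observation index and evaluation of curative effect) gives the measuring rule: "IC is the straight line distance from AC to BD (mm"). The landmarks come from the RBL entry in the same section: "Locate the reference point at the deepest PD site of the affected tooth: cemento-enamel junction (CEJ), alveolar crest (AC), bone defect (BD").

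IC then feeds one of the two percentage formulas: "Defect fill (%) = (preoperative IC- and postoperative IC) / preoperative IC × 100"%.

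Three related facts:
- Section VII ties probing depth to the tooth axis ("paralleling to the long axis of the tooth to measure the distance from the bottom of the periodontal pocket"). It does not do so for IC.
- The defect angle is measured on CBCT at V0, V2 and V3, but no formula uses it.
- Nothing says whether AC at V2 and V3 is the baseline point or is located afresh.

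**The concern.** A height is a distance along the tooth. A point-to-point line from crest to base is a height only if one point lies directly above the other along that axis. In an angular defect the crest stands off from the root by the defect width while the base lies at or near the root, so the line follows the slope of the bony wall. Bone gained vertically shortens only the vertical part of that line.

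Defect fill (%) then depends on how wide the defect was and how its width changed, as well as on how much bone was gained vertically. Defects with the same vertical gain can give different values. That spread goes into the error term of the one-way ANOVA in section VIII, which has no adjustment for angle, in a trial with 26 patients per group. A reader who follows section VI.3 and one who follows section VII could also record different values from the same slice.

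**Working it through.** The plan states no IC value, angle, width, fill percentage or effect size, so there is no figure to reproduce. The check is geometric.

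**Inputs**
- Definition of IC and the fill formula: section VII.
- Depth: section V.1 requires vertical resorption greater than 3 mm. I use h0 = 4 mm; depth cancels except where crest loss is given in mm.
- Defect angle θ: not given, so assumed.
- BD taken at the root surface: an assumption, since section VII does not place it laterally.

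**Formulas.** Let h be vertical depth along the root and w the horizontal distance from AC to the root, with w0 = h0·tan θ at baseline.
- IC = √(h² + w²)
- Vertical fill = (h0 − h1)/h0
- Plan's fill = 1 − √(h1² + w1²)/√(h0² + w0²)

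**Case A: crest and width unchanged, base rises 50% (4 mm to 2 mm)**

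| θ | w | IC before | IC after | Plan's fill |
|---|---|---|---|---|
| 20° | 1.456 | 4.257 | 2.474 | 41.9% |
| 30° | 2.309 | 4.619 | 3.055 | 33.9% |
| 45° | 4.000 | 5.657 | 4.472 | 20.9% |

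Depths of 3 and 6 mm give the same percentages.

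**Case B: width shrinks in proportion to depth.** Both terms scale by 0.5, so a true 50% reads 50.0% at every angle.

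**Case C: width falls 75% while depth falls 50%.** The reading is 53.5% at 25° and 60.5% at 45°: overstated.

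**Case D: base rises 2 mm, width unchanged, crest resorbs 1 mm and is located afresh.** The remaining vertical part is 1 mm. Against a base rise of 50%, the plan's fill reads 64.6% at 15° and 52.0% at 25° (overstated), then 36.6% at 37° and 27.1% at 45° (understated). A projected IC with the crest located afresh would read 1 − 1/4 = 75%, so projection alone does not deal with crest movement.

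**Arm difference under Case A.** Suppose true fills of 50% and 65% (assumed).

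| θ | Reads for 50% | Reads for 65% | Difference, from a true 15 points |
|---|---|---|---|
| 20° | 41.9% | 52.6% | 10.7 |
| 30° | 33.9% | 41.5% | 7.7 |
| 45° | 20.9% | 25.1% | 4.1 |

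(Differences are taken before rounding.) With angles uniform from 20° to 45° (assumed), the mean readings are 31.6% and 38.7%, a difference of 7.1 points. Angle alone gives defects with an identical true 50% fill a reading SD of about 6 points, and about 8 points at 65%.

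**What this does to the standardised difference.** The spread of true fill is compressed too, so the raw shrinkage overstates the loss. Under the same model, with true fill clipped to 0–100%:

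| Assumed SD of true fill | True standardised difference | Using the plan's IC | Loss |
|---|---|---|---|
| 10 points | 1.50 | 0.81 | 46% |
| 20 points | 0.75 | 0.57 | 24% |
| 25 points | 0.60 | 0.48 | 20% |

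**The case against.** The strongest reply is that the fault may be one of wording. The text reads as a rough translation, section VI.3 says height, section V.1 speaks of vertical bone loss, and the straight-line phrase is used for RBL as well, so a vertical measurement may be what was meant. That is possible, but nothing says so, and the only measuring rule for IC is the point-to-point one. The reply lowers confidence that readers will draw the slanted line; it does not remove the conflict between the two sections.

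The second reply concerns direction, and it stands. A reader might infer that Defect fill (%) always understates. That needs a fixed crest, a constant width and BD at the root, and the documents set none of these. Cases B to D show the bias vanishing or reversing. It also vanishes under Case A's fixed crest if the defect fills with a flat floor and BD is marked where the floor meets the bony wall. Nor can one infer that a completely filled defect would read well short of 100%: that requires the reader to record a horizontal line from the old crest to the root as residual IC, which section VII does not ask for.

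Third, the consequence is limited. Defect fill is not designated primary. RBL runs from CEJ to BD and does not use AC, and reconstructed bone volume addresses the stated aim directly. The rule is the same in every arm and the measurers are blinded. The recorded angle would also allow a correction from planned data, although none is planned. All of this stands.

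**Conclusion.** The point holds in conditional form. The label and the definition of IC disagree, and followed literally the definition makes Defect fill (%) a mixture of vertical fill and defect width. With crest and width unchanged and the base rising along the root, a true 50% reads about 42%, 34% or 21% at 20, 30 or 45 degrees. Other patterns of healing give no bias or overstatement, and the plan's fill percentage alone cannot show which applies.

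The main harm is dilution of the arm difference and added noise. A reader might infer that one arm is favoured; the documents do not support this, because the rule is common to all arms. Only an imbalance in defect angles or in healing pattern would shift the comparison, and simple unstratified randomisation leaves the former to chance. Nor is a halving of the raw difference a halving of sensitivity: under the assumed model the standardised difference falls by 20% to 46% over the SDs tried.

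All angles, SDs and true fills here are assumptions, so the size in this trial cannot be set from the documents. This is a cheap improvement to a response measure, not a threat to the whole trial.

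**What to change.** In section VII, define IC as the distance along the tooth long axis from the perpendicular projection of AC on the root to BD. State that AC is held at its baseline position relative to CEJ for the readings at V0, V2 and V3, and that this IC is the one used in Defect fill (%). Reword section VI.3 to agree.

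Both parts are needed: the projection removes the width term, and the fixed reference stops crest loss from counting as fill. With both in place, a true 50% vertical fill reads 50% at any angle.

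The cost is a sentence or two in section VII, a matching edit in section VI.3 and one extra construction line per reading. The scans, slices and readers stay the same, and images already acquired can be re-read.

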promote angiogenesis, inhibit osteoclasts, facilitate the migration and proliferation of gingival fibroblasts, and provide a good microenvironment for the repair and regeneration of traumatic tissue. On the other hand, in 2006, Sacco et al used inner wall coating test tube with silica, concentrated growth factor (CGF) was prepared after differential centrifugation. CGF uses differential centrifugation technology, so the fibrin clot obtained is larger than platelet-rich fibrin (PRF), and the content of fibrin is more. The three-dimensional fibrin network structure of CGF can be observed under scanning electron microscope, red blood cells and platelets are fixed in the fiber network, and the fiber of CGF is thicker and more regular than PRF. The contents and release rules of key growth factors in APRF/CGF were compared, and it was found that both APRF and CGF could stably release higher concentrations of growth factors PDGF- α β , TGF- β and VEGF, while APRF released more and more sustained growth factors than CGF in the later stage, suggesting that APRF may have better structure and function of promoting tissue repair and regeneration than CGF. However, there is no significant difference in the efficacy of APRF and CGF platelet concentrates in periodontal regeneration surgery, and there are some defects such as low level of evidence, small number of case samples, short observation period and so on. At present, there are still few studies on the application of the two in the treatment of clinical periodontal tissue regeneration, and there is no report on comparing the clinical effects of the two through randomized clinical controlled trials.

Based on this, this study compares the clinical application of GTR combined

with APRF/CGF and simple GTR in promoting periodontal bone defect regeneration through randomized clinical controlled trials, and intends to further explore the efficacy of the three methods in improving the amount of alveolar bone regeneration, so as to provide a certain basis for future clinical work.

II. The purpose of the clinical trial

The purpose of this study is to compare the clinical application of GTR combined with APRF/CGF and simple GTR in promoting periodontal bone defect regeneration, and to further explore the efficacy of the three methods in improving the amount of alveolar bone regeneration, so as to provide a basis for future clinical work.

III. Study design

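### Regenerated bone volume is compared between arms without adjustment for the V0 defect volume, which costs precision and leaves chance imbalance in defect size uncorrected

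*Combined protocol and SAP*

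**What the plan says.** - **Aim (Section II).** The trial is "to further explore the efficacy of the three methods in improving the amount of alveolar bone regeneration". No outcome is named primary.
- **Volumetric outcome (Section VII, regenerated bone volume parameters).** Bone models from before and after surgery are combined, "calculated by Boolean operation to obtain the model of regenerated alveolar bone and its volume was measured". No denominator and no unit are given.
- **Linear radiographic outcomes (Section VII).** Both are scaled to the starting value: "Defect fill (%) = (preoperative IC- and postoperative IC) / preoperative IC × 100" and "Defect resolution (%) = (preoperative RBL- and postoperative RBL) / preoperative RBL × 100".
- **Baseline (Section VI.3).** At V0, "the volume of intraosseous defect was measured after three-dimensional reconstruction of the affected teeth".
- **Follow-up (Section VII).** At 24 and 48 weeks, "the researchers measured PD, CAL, mobility, BOP, RBL, IC, intraosseous defect angle and bone defect volume".
- **Analysis (Section VIII).** Baseline data are compared between arms. Efficacy is compared by one-way ANOVA, or by rank tests if normality and equal variance fail. No covariate appears in either.
- **Design (Sections III, V.1 and VI.1).** Simple randomisation, 26 per arm, no stratification by defect size. Entry requires vertical bone loss above 3 mm and sets no upper limit.

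**The concern.** The bone that can fill a defect is limited by the size of that defect, so part of the spread in regenerated volume reflects how large the defect was at the start. Entry sets only a lower limit on depth, so starting volumes are free to vary, although the documents give no figure for how much. The plan scales its linear indices to the starting value but does nothing comparable for volume, the measure closest to its aim. Regenerated volume is zero by construction at V0, so it has no baseline of its own to adjust for; the natural covariate is V0 defect volume, which is already collected.

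Two things are at stake. Variation in defect size sits in the error term and can hide a real treatment difference. And if one arm happens to receive larger defects, the planned analysis does not correct for it.

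**Working it through.** **Inputs from the documents.** 26 per arm, 3 × 26 = 78 (Section VI.1); significance level 0.05 (Section VIII). There is no effect size, SD, power or sample-size calculation, so there is no planned figure to reproduce. Everything below about defect-volume spread, fill and correlation is assumed.

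**1. Pairwise precision** (normal approximation, two-sided 0.05 assumed, 80% power).
Unadjusted detectable difference = √(2/26) × (1.960 + 0.842) = 0.277 × 2.802 = 0.78 SD.
Adjusting for a baseline that has correlation r with the outcome multiplies this by √(1 − r²). The equivalent unadjusted sample is 26/(1 − r²).

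| r | Detectable difference (SD) | Power at 0.78 SD | Equivalent n per arm |
|---|---|---|---|
| 0 | 0.78 | 80% | 26 |
| 0.3 | 0.74 | 84% | 29 |
| 0.5 | 0.67 | 90% | 35 |
| 0.7 | 0.55 | 97% | 51 |
| 0.8 | 0.47 | >99% | 72 |

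**2. Error rate with no treatment effect.** Simulation of 3 × 26: V0 volume lognormal with mean 100, share filled 50% with SD 15 points, outcome = V0 volume × share. At CV 30/50/70%, ANOVA on raw volume rejected in 5.0/5.0/4.3% of trials. The nominal level is kept.

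**3. Power if regeneration is proportional to defect size.** Same model, with mean share filled 50/50/60% in the three arms.

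| Analysis | CV 30% | CV 50% | CV 70% |
|---|---|---|---|
| Raw volume, ANOVA | 34% | 20% | 12% |
| ANCOVA on V0 defect volume | 63% | 59% | 52% |
| Percentage fill, ANOVA | 67% | 69% | 68% |

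With SD 20 points the loss is smaller: raw 27/17/12%, ANCOVA 39/35/31%, percentage fill 43–44%. With a larger effect (50% against 62% in both platelet arms, SD 15 points): raw 46/24/15%, ANCOVA 80/75/68%, percentage fill 84%. In this model the within-arm correlation of V0 volume with regenerated volume is about 0.67/0.82/0.88, so defect size accounts for 0.67² = 45% to 0.88² = 77% of the variance in raw volume.

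**4. Power if regeneration is mostly not proportional.** Assumed alternative: regenerated volume = 40 + 0.1 × V0 volume, plus 10 in one arm, SD 15, capped at V0 volume.

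| Analysis | CV 30% | CV 50% | CV 70% |
|---|---|---|---|
| Raw volume, ANOVA | 64% | 51% | 36% |
| ANCOVA on V0 defect volume | 67% | 60% | 50% |
| Percentage fill, ANOVA | 43% | 28% | 20% |

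Percentage fill goes from best to worst. ANCOVA beats raw volume in both models.

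**5. Chance imbalance.** The standard error of a baseline difference between two arms is √(2/26) = 0.28 SD. For any one pair, the chance of a difference above 0.3 SD is 28%, and above 0.5 SD it is 7%. At CV 30/50/70%, the largest arm-mean V0 volume exceeds the smallest by 20% or more in 7/39/61% of trials. Among such trials with no treatment effect, raw volume rejects in 23/12/8%, against about 4–6% for percentage fill. The 5% overall rate already averages over these trials.

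**The case against.** The strongest reply is that randomisation already deals with defect size. A reader might infer from the missing denominator that defect size, not treatment, decides the result. The documents do not support that. Allocation is random, the unadjusted comparison is unbiased in expectation, and step 2 shows its error rate is held. The baseline gaps in step 5 describe imbalance, not wrong conclusions on average.

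A reader might also infer that only a percentage outcome is valid. That does not follow either. The aim concerns an amount of bone, which an absolute volume answers directly, and step 4 shows that a ratio can do worse than the planned analysis. The proportional model in step 3 favours the ratio by construction, since the treatment acts on the share and the share is independent of size.

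Nor does the plan ignore defect size altogether. Baseline data are compared between arms, defect volume is measured again at 24 and 48 weeks, so its change could be analysed, and two other radiographic outcomes are baseline-scaled. This concerns one outcome among several.

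All of that stands, and it limits the point to precision and chance imbalance. It does not remove it. Comparing baselines describes an imbalance without correcting the outcome, and no stated analysis links V0 defect volume to regenerated volume.

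**Conclusion.** The concern holds as one of precision and uncorrected chance imbalance, not of bias or a raised false-positive rate. In the scenarios run, leaving out V0 defect volume lowers three-arm power from 63/59/52% to 34/20/12% in the proportional model (SD 15 points), and from 67/60/50% to 64/51/36% in the mostly non-proportional one. The loss therefore ranges from a few points to about 40, depending on the spread of defect volumes and on how closely regeneration follows defect size. The documents give neither, so these figures illustrate the range and do not predict this trial's power. ANCOVA had more power than raw volume in every scenario with a treatment effect. Percentage fill did not.

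**What to change.** In Section VIII, prespecify the between-arm comparison of regenerated bone volume at 24 and 48 weeks as an ANCOVA with arm as factor and V0 defect volume as covariate. Base the pairwise comparisons on the adjusted means and check the distributional assumptions on the residuals.

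In Section VII, add volumetric fill (%) = regenerated volume / V0 defect volume × 100, alongside the existing "Defect fill (%) = (preoperative IC- and postoperative IC) / preoperative IC" index. Label it supporting and do not let it replace the absolute volume. It will be noisy in very small defects and can lose power if regeneration is not proportional to defect size.

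The cost is one covariate, one formula and one degree of freedom. Both volumes are already planned, so no extra scans or patients are needed.

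### If the alveolar crest is located afresh on each follow-up scan, the Defect fill percentage counts crest resorption as fill, because neither the crest nor the measurement site is fixed at baseline

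*Combined protocol and SAP*

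**What the plan says.** Section VII of the combined protocol and SAP names three landmarks, placed at the site of greatest probing depth on the affected tooth: the cemento-enamel junction (CEJ), the alveolar crest (AC) and the bone defect (BD). Two distances follow: "RBL is the straight line distance from CEJ to BD (mm" and "IC is the straight line distance from AC to BD (mm".

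Each distance feeds one percentage: "Defect fill (%) = (preoperative IC- and postoperative IC) / preoperative IC", and "Defect resolution (%) = (preoperative RBL- and postoperative RBL) / preoperative RBL", both multiplied by 100.

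At baseline, section VI.3 (Treatment scheme) says "the height of bone defect (IC), bone level (RBL) and the angle of intraosseous defect were measured by CBCT image". Section VII repeats the measurements at 24 and 48 weeks: "the researchers measured PD, CAL, mobility, BOP, RBL, IC, intraosseous defect angle and bone defect volume". Section VI.3 also calls for duplicate readings, averaged, and a consistency test of the measurers.

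No section says that the preoperative crest is carried forward to the later scans. None says whether the site of greatest probing depth is the baseline site or is chosen again at each visit. The CEJ-to-crest distance is not listed as an outcome.

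**The concern.** Both ends of IC are bone landmarks, so both can move after surgery. A fall in IC can mean that bone formed at the base of the defect, that the crest was lost, or some of each, and the formula does not separate them. Duplicate readings and consistency tests control reading error; they do nothing about crest movement.

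Section II states the aim as to "further explore the efficacy of the three methods in improving the amount of alveolar bone regeneration", and a percentage called Defect fill will be read as a measure of that. If the crest is relocated on each scan, a tooth that only lost crest height would be reported as partly filled, and a tooth that gained crest height would be marked down. The plan names no primary endpoint, so nothing in the text ranks this percentage below the others.

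**Working it through.** **Inputs.** The formulas and definitions are those of section VII. The plan gives no computed value of fill to reproduce, and no figures for IC, CEJ-to-crest distance or crest change. The only related figure is the entry criterion in section V.1 of vertical bone resorption greater than 3 mm. The millimetre values below are therefore assumptions that show the mechanism; they do not predict this trial's results.

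**Algebra.** Take CEJ, AC and BD as collinear and let C be the CEJ-to-crest distance, so RBL = C + IC. Write 0 for preoperative and 1 for postoperative, g for gain at the base and c for loss at the crest (negative for crest gain). With AC located again at follow-up:

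- RBL1 = RBL0 − g, and C1 = C0 + c
- IC1 = RBL1 − C1 = IC0 − g − c
- Defect fill as written = (IC0 − IC1)/IC0 = (g + c)/IC0
- RBL-based fill = (RBL0 − RBL1)/IC0 = g/IC0
- Defect resolution = g/RBL0, which does not contain c

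**Example.** IC0 = 5 mm and C0 = 2 mm, so RBL0 = 7 mm.

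| Base gain (mm) | Crest change (mm) | IC1 | RBL1 | Defect fill as written | RBL-based fill | Defect resolution |
|---|---|---|---|---|---|---|
| 0 | 1 lost | 4 | 7 | 20% | 0% | 0% |
| 2 | 1 lost | 2 | 5 | 60% | 40% | 28.6% |
| 2 | none | 3 | 5 | 40% | 40% | 28.6% |
| 2 | 0.5 gained | 3.5 | 5 | 30% | 40% | 28.6% |

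The last three rows have the same gain at the base, yet fill as written runs from 30% to 60%.

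**Range.** With no gain at the base, fill as written is c/IC0. For IC0 of 4 to 6 mm and crest loss of 0.5 to 1 mm, it runs from 0.5/6 = 8.3% to 1/4 = 25.0%. At the 3 mm entry limit, 1 mm of crest loss gives 33.3%. A crest gain of 0.5 mm lowers fill by 8.3 points (IC0 6 mm) to 12.5 points (IC0 4 mm).

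**Oblique line.** The direction does not depend on collinearity. With a 2 mm horizontal offset between AC and BD and no gain at the base, IC is √(vertical depth² + 2²). At 3 mm depth, 1 mm of crest loss gives (√13 − √8)/√13 = 21.6%. At 5 mm depth it gives (√29 − √20)/√29 = 17.0%. A crest gain of 1 mm gives −24.0% and −17.4%.

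**Limit of the RBL-based ratio.** Assume BD lies on a straight root surface, vertical depth 5 mm, stable crest, and angle θ between the root and the AC–BD line. Then IC0 = 5/cos θ. For a base gain of 2 mm the vertical fill is 2/5 = 40%. The RBL-based ratio reads 0.4 × cos θ, which is 37.6% at 20° and 30.6% at 40°. The formula as written reads 34.1% and 21.0%. At complete fill the RBL-based ratio reads cos θ, about 94% and 77%; the formula as written reads 1 − sin θ, about 66% and 36%.

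**The case against.** The strongest reply is that the document does not say the crest is relocated. If the preoperative crest were carried forward, then with collinear landmarks the formula as written would equal (RBL0 − RBL1)/IC0 and the problem would vanish. This stands as a condition on the finding. But section VII lists IC among the distances measured again at 24 and 48 weeks, so a fresh location on each scan is the natural reading. If the other is meant, the text must say so, and an edit is needed either way.

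A second reply is that section VI.3 calls IC the height of the bone defect, so the ratio is a proportional fall in defect height. As a description of the arithmetic that is right, and it is a reason to keep the ratio under such a name. It does not justify calling it fill.

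A third reply is that regeneration is measured elsewhere. Section VII also has a volume measure: "The volume of alveolar bone before and after operation was calculated by Boolean operation". RBL and Defect resolution do not use AC either, and in the example with crest loss alone Defect resolution would show 0% beside 20% fill. This stands and limits the harm, although none of these measures corrects the fill percentage.

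A reader might also infer that Defect resolution is wrong, because its denominator includes the CEJ-to-crest distance. The documents do not support that. Its formula is fully stated, its numerator and sign are sound, and any complaint concerns only its name.

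**Conclusion.** The point holds in conditional form. If AC is located again at follow-up and the landmarks are roughly collinear, Defect fill equals (base gain + crest loss)/IC0. Under the assumed dimensions, crest loss of 0.5 to 1 mm alone reads as about 8% to 25% fill for defects of 4 to 6 mm, and 0.5 mm of crest gain takes off about 8 to 13 points. The direction follows from the plan's own definitions; the size depends on crest changes that the documents do not give.

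A reader might infer that the comparison of the three arms is biased. The documents do not show this. It would need crest change to differ by arm, which they neither report nor predict; because crest change occurs after randomisation, balance cannot be assumed either. Nor do they support a claim of lost precision, since the effect on variance depends on an unknown correlation between crest change and base gain. The fault is confined to IC and the percentage derived from it. It is a modest point, worth settling before results are analysed so that the definition is not chosen with the data in view.

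**What to change.** In section VII, define Defect fill (%) = (RBL0 − RBL1)/IC0 × 100, and state that RBL and IC are measured at every visit at the site that was deepest on probing at baseline. The site rule is essential: if the site is chosen again at each visit, RBL0 and RBL1 may come from different sites and their difference is no longer the gain at the base.

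Keep (IC0 − IC1)/IC0 only as relative reduction in defect depth, with a note that it includes crest change. State how AC is located at follow-up, and report the change in CEJ-to-crest distance by arm.

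The cost is a few lines of text and one extra distance between landmarks already located on CBCT images planned at baseline, 24 and 48 weeks. No new visit or scan is needed. Reported fill may be lower where the crest is lost. Because the distances are straight lines, the new ratio still understates fill in wide-angled defects, though by less than the present formula does with a stable crest.
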